13.2. Visual Function Questionnaires

13.2.1. National Eye Institute Visual Function Questionnaire-25 (NEI-VFQ-25)

The NEI-VFQ-25 consists of a base set of 25 vision-targeted questions representing 11 vision-related constructs, plus an additional single-item general health rating question [Mangione, 2001]. The NEI-VFQ-25 generates the following vision-targeted sub-scales: global vision rating, difficulty with near vision activities; difficulty with distance vision activities; limitations in social functioning due to vision; role limitations due to vision; dependency on others due to vision; mental health symptoms due to vision; driving difficulties; limitations with peripheral vision, limitations with color vision; and ocular pain. Details of deriving domain scores and overall composite score can be found in Section 16.6.5.3.

For each of 11 sub-scale scores, the descriptive summary of the actual value and change from baseline by visit will be provided. The overall composite score and 11-sub-scale scores will be listed.

13.2.2. Ocular Surface Disease Index

The Ocular Surface Disease Index (OSDI) is a 12-item questionnaire designed to assess both the frequency of dry eye symptoms and their impact on vision-related functioning [Schiffman, 2000]. The OSDI has demonstrated good reliability, validity, sensitivity, and specificity, and can be used as a complement to other clinical and subjective measures of dry eye disease by providing a quantifiable assessment of dry eye symptom frequency and the impact of these symptoms on vision-related functioning.

For the OSDI, the total score will be calculated as well as scores for the three subscales (ocular symptom: item 1-3; vision-related function: item 4-9; and environmental triggers: item 10-12).

The total OSDI score = ([sum of scores for all questions answered \times 100]/[total number of questions answered \times 4]). Subscale scores are computed similarly with only the questions from each subscale used to generate its own score. Subscale scores are computed similarly with only the questions from each subscale used to generate its own score. A score of 100 corresponds to complete disability (a response of “all of the time” to all questions answered), while a score of 0 corresponds to no disability (a response of “none of the time” to all questions answered). Therefore, decrease in score from baseline means improvement.

For each of the three sub-scales, the descriptive summary of the actual value and change from baseline at selected time points will be provided. For the Vision-Related Functioning domain, the number and percentage of participants with post-baseline score worsening of ≥ 12.5 from baseline score will be summarized at selected time points. Additionally, a time to event analysis of time to meaningful worsening based on the ≥ 12.5 threshold will be summarized with frequency of number of patients with event (N, %). Time to first event and duration of event will also be calculated (median days, range). Additionally, recovery from first event defined as ≥ 12.5 decrease from the first worst score will be summarized.

Plots of mean change from baseline (including baseline) and 95% confidence interval over time by visit, and at end of study treatment, last follow-up, and worst case post-baseline for individual domains will also be provided. The overall total score and sub-scale scores will be listed.

13.3. Value Evidence and Outcome (Part 2 only)

13.3.1. European Organization for Research and Treatment of Cancer Quality of Life Questionnaire 30-item Core module (EORTC QLQ-C30)

The EORTC QLQ-C30 is a 30-item questionnaire containing both single- and multi-item measures [Aaronson, 1993]. These include five functional scales (Physical, Role, Cognitive, Emotional, and Social Functioning), three symptom scales (Fatigue, Pain, and Nausea/Vomiting), a Global Health Status/QoL scale, and six single items (Constipation, Diarrhea, Insomnia, Dyspnea, Appetite Loss, and Financial Difficulties). Scores for each scale and single-item measure are averaged and transformed linearly to a score ranging from 0–100. Details of deriving domain scores (9 scales and 6 single items) and summary score can be found in Section [16.6.5.1](#).

A high score for functional scales and for Global Health Status/QoL represent better functioning ability or Health-Related Quality of Life (HRQoL), (higher score indicates improvement) whereas a high score for symptom scales and single items represents significant symptomatology [Proskorovsky 2014]. (lower score indicates improvement)

Descriptive summaries (mean, SD, median, min and max) of the actual value and change from baseline at selected time points will be provided for EORTC QLQ-C30 summary score and each domain score.

Plots of mean change from baseline (including baseline) and 95% confidence interval over time by visit, and at end of study treatment, last follow-up, and worst case post-baseline for individual domains will also be provided. The overall summary score and 11-sub-scale scores will be listed.

13.3.2. European Organization for Research and Treatment of Cancer Quality of Life Questionnaire 20-item Multiple Myeloma module (EORTC QLQ-MY20)

The EORTC QLQ-MY20 is a supplement to the QLQ-C30 instrument used in patients with multiple myeloma [Aaronson, 1993; Cocks, 2007]. The module comprises 20 questions that address four myeloma-specific HRQoL domains: Disease Symptoms, Side Effects of Treatment, Future Perspective, and Body Image. Three of the four QLQ-MY20 domains are multi-item scales: Disease Symptoms (includes bone aches or pain, back pain, hip pain, arm or shoulder pain, chest pain, and pain increasing with activity); Side Effects of Treatment (includes drowsiness, thirst, feeling ill, dry mouth, hair loss, upset by hair loss, tingling hands or feet, restlessness/agitation, acid indigestion/heartburn, and burning or sore eyes); and Future Perspective (includes worry about death and health in the future, and thinking about illness). The Body Image scale is a single-item scale that addresses physical attractiveness. Details of deriving domain scores can be found in Section 16.6.5.2.

For each of four domain scores, a descriptive summary of the actual value and change from baseline by visit will be provided:

Plots of mean change from baseline (including baseline) and 95% confidence interval over time by visit, and at end of study treatment, last follow-up, and worst case post-baseline for individual domains will also be provided. The 4-domain scores will be listed.

13.4. Compliance of OSDI, EORTC QLQ-C30, and EORTC-QLQ-MY20

Tables to summarize the compliance of OSDI (Part 1 and Part 2) and EORTC QLQ-C30 and EORTC-QLQ-MY20 (Part 2 only) by visit will be provided. The Tables will include number of subjects remaining in study, number and percentage of participants with OSDI summary score, QLQ-C30 summary score, and QLQ-MY20 summary score. The percentage is calculated using number of participants remaining in the study at given timepoint as denominator.

14. ADDITIONAL ANALYSES DUE TO THE COVID-19 PANDEMIC

14.1. Study Population

14.1.1. Subject Disposition

A summary of recruitment by country and site, relative to COVID-19 Pandemic measures will be produced. For the definition of the phases of the COVID-19 pandemic measures see Section 16.4.1.4.

A country level listing of the dates of the COVID-19 Pandemic measures, will be produced. The ‘Summary of Subject Status and Reason for Study Withdrawal’ and the ‘Summary of Treatment Status and Reasons for Discontinuation of Study Treatment’ will be repeated, with the reason for withdrawal/discontinuation categorised as due to the COVID-19 pandemic, or non-due to the COVID-19 pandemic based on information collected on the COVID-19 Pandemic Study Impact form. The summaries will be based on GSK Core Data Standards, and details are provided in [Appendix 11: List of Data Displays](#).

14.1.2. Protocol Deviations

In addition to the overall summary of important protocol deviations, separate summaries will be produced of important protocol deviations related to COVID-19, and non-important protocol deviations related to COVID-19. A listing of important protocol deviations related to COVID-19 will also be produced.

The summaries will be based on GSK Core Data Standards, and details are provided in [Appendix 11: List of Data Displays](#).

14.1.3. Additional Displays for Participants with a COVID-19 Infection

A participant is defined as having a suspected, probable or confirmed COVID-19 infection during the study if the answer is “Confirmed”, “Probable” or “Suspected” to the case diagnosis question from the COVID-19 coronavirus infection assessment eCRF.

Summaries and listings of the numbers of participants with a suspected, probable or confirmed COVID-19 infection, and of COVID-19 test results will be based on GSK Core Data Standards. The details of the planned displays are provided in [Appendix 11: List of Data Displays](#).

Additionally, if greater than 5 participants have a suspected, probable or confirmed COVID-19 infection, the following data displays will be produced:

- Summary of COVID-19 Assessments for Subjects with Suspected, Probable or Confirmed COVID-19 Case Diagnosis

- Summary of COVID-19 Symptoms for Subjects with Suspected, Probable or Confirmed COVID-19 Case Diagnosis

All of the above displays will be based on GSK Core Data Standards. The details of the planned displays are provided in [Appendix 11: List of Data Displays](#).

14.2. Safety

14.2.1. Assessment of COVID-19 AEs

A Standardised MedDRA Query (SMQ) will be used to identify all COVID-19 AEs.

The incidence of AEs of COVID-19, and COVID-19 AEs leading to study drug discontinuation will be obtained from standard AE summaries.

If $>5\%$ participants report ≥ 1 COVID-19 AEs, then the following data displays will be produced:

- Summary of COVID-19-Related Adverse Events by System Organ Class and Preferred Term and Maximum Grade
- Summary of COVID-19 Adverse Events Leading to Permanent Discontinuation of Study Treatment by Overall Frequency
- Listing of COVID-19 Adverse Events
- Listing of COVID-19 Assessments and Symptom Assessments for Subjects with COVID-19 Adverse Events

All of the above displays will be based on All of the above displays will be GSK Core Data Standards. The details of the planned displays are provided in [Appendix 11: List of Data Displays](#).

16. APPENDICES

16.1. Appendix 1: Protocol Deviation Management and Definitions for Per Protocol Population

This study does not have per protocol population.

16.2. Appendix 2: Schedule of Activities

16.2.1. Protocol Defined Schedule of Events

Refer to Section 7 of Protocol (Version: GSK Document Number [TMF-14344600](#)).

16.3. Appendix 3: Assessment Windows

No assessment windows will be applied.

16.4. Appendix 4: Study Phases and Treatment Emergent Adverse Events

16.4.1. Study Phases

Assessments and events will be classified according to the time of occurrence relative to Screening Assessment, On Study Assessment Completed Independent of Dosing, On study Assessment with Dosing Days (Cycles), and End of Study and Follow-up Assessment.

Study Phase	Definition
Pre-Treatment	Date \leq Study Treatment Start Date
On-Treatment	Study Treatment Start Date $<$ Date \leq Study Treatment Stop Date + 30 days For interim analyses when subjects are still on treatment, Study Treatment Stop Date will be imputed following rules specified in Section 16.7.2.1
Post-Treatment	Date $>$ Study Treatment Stop Date + 30 days

16.4.1.1. Study Phases for Concomitant Medication

Study Phase	Definition
Prior	End Date $<$ Study Treatment Start Date
Post-Treatment	Start Date $>$ Study Treatment Stop Date + 30 days For interim analyses when subjects are still on treatment, Study Treatment Stop Date will be imputed following rules specified in Section 16.7.2.1.
Concomitant	If the medication is not Prior nor Post-treatment

NOTES:

- Please refer to [Appendix 7](#): Reporting Standards for Missing Data for handling of missing and partial dates for concomitant medication. Use the rules in this Table if concomitant medication date is missing.

16.4.1.2. Study Phases for Vital signs, ECG and Laboratory Values

Study Phase	Definition
Pre-Treatment	Date \leq Study Treatment Start Date (if time is collected then Date/time \leq Study Treatment Start Date/time)
On-Treatment	Study Treatment Start Date $<$ Date (if time is collected then Date/time $>$ Study Treatment Start Date/time)

NOTES:

- If the study treatment stop date is missing, then the AE will be considered to be On-Treatment.
- Time of study treatment dosing and start/stop time of vital signs, ECG, and laboratory values should be considered, if collected.

16.4.1.3. End of Treatment Exposure

Study Phase	Definition
Post-Treatment	Date $>$ Study Treatment Stop Date + 20 days

16.4.1.4. Phases of COVID-19 Pandemic Measures

Pandemic measures began in different countries at different times. A dataset containing the date when pandemic measures began, as determined by the GSK country Issue Management Teams (IMT), and available within the HARP reporting environment (arcomm folder), will be used to determine the start date of pandemic measures within each country. A copy of this dataset will be taken at the time of database lock (DBL).

Adverse events will be summarised according to whether the onset date was before or after the start of the COVID-19 pandemic measures.

Pandemic Measures Phase	Definition
Before	AE onset date < pandemic measures start date
After	Pandemic measures start date ≤ AE onset date

16.4.2. Treatment Emergent Flag for Adverse Events

Flag	Definition
Treatment Emergent	
 If AE onset date is on or after treatment start date or missing 
 Study Treatment Start Date ≤ AE Start Date ≤ Study Treatment Stop Date + 45 days AE Start Date is missing

NOTES:

- If the study treatment stop date is missing, then the AE will be considered to be On-Treatment.
- Time of study treatment dosing and start/stop time of AEs should be considered, if collected.

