8.7. Clinical Laboratory Analyses

Laboratory evaluations including the analyses of Chemistry laboratory tests, Hematology laboratory tests, Urinalysis, and liver function tests will be based on GSK Core Data Standards. The details of the planned displays are in [Appendix 11: List of Data Displays](#).

Summary of change from baseline by scheduled visits using mean, median, standard deviation, minimum and maximum will be provided.

Summaries of worst case grade increase from baseline grade will be provided for all the lab tests that are gradable by CTCAE v4.03. These summaries will display the number and percentage of subjects with a maximum post-baseline grade increasing from their baseline grade. Any increase in grade from baseline will be summarized along with any increase to a maximum grade of 3 and any increase to a maximum grade of 4. The 'Any Grade Increase' column will include all cases where the worst-case grade is 1 or higher and the baseline grade is missing. Likewise the Increase to Grade X (where X=3 or 4) will include cases that are worst-case grade X and the baseline grade is missing. Missing baseline grade will be assumed as grade 0. For laboratory tests that are graded for both low and high values, summaries will be done separately and labelled by direction, e.g., sodium will be summarized as hyponatremia and hypernatremia.

For lab tests that are not gradable by CTCAE v4.03, summaries of worst case changes from baseline with respect to normal range will be generated. Decreases to low, changes to normal or no changes from baseline, and increases to high will be summarized for the worst case post-baseline. If a subject has a decrease to low and an increase to high during

the same time interval, then the subject is counted in both the “Decrease to Low” categories and the “Increase to High” categories.

For urinalysis laboratory tests results, occult blood, proteins, ketones, and glucose dipstick tests will be summarized. If the subject has a discrete value greater than 0 or a character value that is positive, then the subject is counted in the “Presence” category. Otherwise, the subject is counted in the “Absence” category.

The number of subjects with worst case urinalysis laboratory tests results will be summarized by the combination of specimen, method, test, and category. Subjects with a missing baseline value are to be assumed to have a negative baseline value.

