Adverse Events	
 Imputations in the adverse events dataset are used for slotting events to the appropriate study time periods and for sorting in data listings. Partial dates for AE recorded in the CRF will be imputed using the following conventions: 
 
 Missing start day	 
 If study treatment start date is missing (i.e. participant did not start study treatment), then set start date = 1st of month. Else if study treatment start date is not missing: 
 If month and year of start date = month and year of study treatment start date then 
 If stop date contains a full date and stop date is earlier than study treatment start date then set start date = 1st of month. Else set start date = study treatment start date. Else set start date = 1st of month. 	
 
 Missing start day and month	 
 If study treatment start date is missing (i.e. participant did not start study treatment), then set start date = January 1. Else if study treatment start date is not missing: 
 If year of start date = year of study treatment start date then 
 If stop date contains a full date and stop date is earlier than study treatment start date then set start date = January 1. Else set start date = study treatment start date. Else set start date = January 1. 	
 
 Missing stop day	Last day of the month will be used.	
 
 Missing stop day and month	No Imputation	
 
 Completely missing start/end date	No imputation	
 
	Missing start day	
 If study treatment start date is missing (i.e. participant did not start study treatment), then set start date = 1st of month. Else if study treatment start date is not missing: 
 If month and year of start date = month and year of study treatment start date then 
 If stop date contains a full date and stop date is earlier than study treatment start date then set start date = 1st of month. Else set start date = study treatment start date. Else set start date = 1st of month. 	Missing start day and month	
 If study treatment start date is missing (i.e. participant did not start study treatment), then set start date = January 1. Else if study treatment start date is not missing: 
 If year of start date = year of study treatment start date then 
 If stop date contains a full date and stop date is earlier than study treatment start date then set start date = January 1. Else set start date = study treatment start date. Else set start date = January 1. 	Missing stop day	Last day of the month will be used.	Missing stop day and month	No Imputation	Completely missing start/end date	No imputation

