16.11.7. Safety Tables

Safety: Tables					
No.	Population	IDSL / Example Shell	Title	Programming Notes	Deliverable [Priority]
Adverse Events (AEs)					
3.001	All Treated	AE5B	Summary of All Adverse Events by System Organ Class and Preferred Term and Maximum Grade	Report for: Part 1, Part 2, and combined Part 1 and Part 2; ; Summarize by: dose level (Refer to Section 5.1 for ordering of dose level and omit 1.92 mg/kg if data is not available) Total.	P-SAC [3], F-SAC [4]
3.002	All Treated	AE5B	Summary of All Treatment-Emergent Adverse Events by System Organ Class and Preferred Term and Maximum Grade	Report for: Part 1, Part 2, and combined Part 1 and Part 2; ; Summarize by: dose level (Refer to Section 5.1 for ordering of dose level and omit 1.92 mg/kg if data is not available) Total.	P-SAC [3], F-SAC [4]
3.003	COVID-19	AE5B	Summary of All COVID-19 Adverse Events by System Organ Class and Preferred Term and Maximum Grade	Report for: Part 1, Part 2, and combined Part 1 and Part 2; ; Summarize by: dose level (Refer to Section 5.1 for ordering of dose level and omit 1.92 mg/kg if data is not available) Total. only if greater than 5 participants with COVID-19 infection; If less than 5 participants, produce listing instead;	P-SAC [3], F-SAC [4]

Safety: Tables					
No.	Population	IDSL / Example Shell	Title	Programming Notes	Deliverable [Priority]
3.004	All Treated	AE3	Summary of Common (>=5%) Adverse Events by Overall Frequency	Report for: Part 1, Part 2, and combined Part 1 and Part 2; Summarize by: dose level (Refer to Section 5.1 for ordering of dose level and omit 1.92 mg/kg if data is not available) Total.	P-SAC [3], F-SAC [4]

Safety: Tables					
No.	Population	IDSL / Example Shell	Title	Programming Notes	Deliverable [Priority]

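### The treatment-emergent flag (SAP 16.4.2) looks only at the AE start date: it admits an event known to have ended before first dose if the start is wholly missing, and misses on-treatment worsening kept on a pre-dose record

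*SAP*

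**What the plan says.** SAP Section 16.4.2 states the flag as "If AE onset date is on or after treatment start date or missing" and gives two routes to it. The first is a date window, "Study Treatment Start Date ≤ AE Start Date ≤ Study Treatment Stop Date + 45 days". The second is "AE Start Date is missing", with nothing attached to it. Neither route mentions grade or the AE stop date. A note adds: "Time of study treatment dosing and start/stop time of AEs should be considered, if collected".

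This is the only working definition in the document. Section 8.1 sends the reader to 16.4.1.2 for treatment-emergent AEs, but that section covers vital signs, ECG and laboratory values.

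Two other sections bear on the point:

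- Section 16.7.2.1 imputes partial AE start dates. Where the known month and year (or year) match those of first dose, it consults the stop date: "If stop date contains a full date and stop date is earlier than study treatment start date then set start date = 1st of month". The version for a missing day and month sets 1 January instead. A completely missing start date is not imputed.
- Section 8.7 counts worsening from baseline for gradable laboratory tests: "These summaries will display the number and percentage of subjects with a maximum post-baseline grade increasing from their baseline grade".

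The display that uses the flag is Table 3.002 in Section 16.11.7, "Summary of All Treatment-Emergent Adverse Events by System Organ Class and Preferred Term and Maximum Grade".

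**The concern.** A treatment-emergent summary is meant to separate what arose or got worse under treatment from what was there before. A rule that sees only the start date can fail in both directions.

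It can admit an event that the data show was over before the first infusion, simply because nobody recorded when it began. It can also leave out an event that was mild at first dose and became severe on treatment. In the second case the plan's own outputs could disagree: a neutropenia going from Grade 1 to Grade 4 would count as an increase to Grade 4 in laboratory Table 3.0063, while the matching AE could be absent from Table 3.002. Thrombocytopenia is an AE of special interest here and neutropenia an identified risk (Section 8.2), so these are events a reader will look for. There is no control arm against which such misclassification could be compared.

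**Working it through.** The plan states no figure on this point, so the check applies its rules literally to test records.

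**Inputs.** The window and the missing-start route come from 16.4.2, and the partial-date rules from 16.7.2.1. Illustrative dates (assumed, not from the SAP): first dose 10 March 2020, last dose 10 September 2020. The window therefore runs from 10 March to 10 September + 45 days = 25 October 2020.

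**Rule.** Flag = yes if the start is missing after imputation, or if 10 March ≤ start ≤ 25 October. Otherwise no.

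| Record | Start date used | Flag |
|---|---|---|
| A. Start 1 March, Grade 1 rising to Grade 4 on treatment, one record | 1 March | No |
| B. As A, but the worsening entered as a new record dated 1 May | 1 May | Yes |
| C. Start day missing (March 2020), stop 5 March | 1 March (imputed) | No |
| D. Start day and month missing (2020), stop 5 March | 1 January (imputed) | No |
| E. Start completely missing, stop 5 March | missing | Yes |
| F. Start and stop both completely missing | missing | Yes |

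**Missing start date: C and D against E.** All three events ended on 5 March, five days before first dose. For C and D the plan uses that fact and keeps the event before treatment. For E it has the same fact and does not use it. F differs: the timing really is unknown, and counting it as emergent is a defensible default. The note on times does not rescue E. It asks for clock times to be considered where collected and states no exclusion for an event that has already stopped.

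**Worsening: A against B.** The clinical course is the same and only the record structure differs. The result therefore depends on an eCRF convention that the SAP does not state. Section 8.1 does allow for one preferred term recurring in a subject at different grades, which is compatible with several records per episode but does not establish it.

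**Weight of one subject.** Section 2.3 plans about 12 subjects in Part 1 and about 28 in Part 2.

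- Part 2: 1/28 = 3.6 percentage points per row.
- Overall: 1/(12 + 28) = 1/40 = 2.5 points per row.

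This is the weight of any single subject in any table, not an estimate of how many are misclassified.

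**The case against.** The strongest reply is that little depends on Table 3.002, and this largely stands. It is the only listed display titled treatment-emergent, and it is not among the headline results. The headline AE summary, Table 3.0015, states no treatment-emergent restriction. Nor do the all-AE tables such as 3.001, the thrombocytopenia tables (3.0026, 3.0036) or the neutropenia tables (3.0040, 3.0042). The Part 2 safety stopping rule in Section 3.1.2 counts treatment-related Grade 4 or higher AEs without reference to the flag. A reader might infer that the study's safety profile loses on-treatment worsening. The documents do not support that, because the same event remains in these other displays.

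A reader might also infer that a worsening event can never be flagged. Record B shows otherwise.

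Nor does the existence of separate Tables 3.001 and 3.002 prove that pre-dose AEs are in the database. The two also differ through AEs starting more than 45 days after treatment stop. Section 16.7.2.1 provides for AEs that ended before treatment, but nearly the same text serves concomitant medications, and when AE collection begins is a protocol matter.

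Finally, flagging a missing start date can be called conservative, like the worst-case handling of missing relatedness in Sections 8.1 and 8.3. That argument covers record F but not record E, where the stop date settles the timing. The case is narrow, since partial start dates are already handled.

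**Conclusion.** The definition in 16.4.2 needs correcting, within limits.

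- **Missing start date.** This holds whatever the eCRF convention. An AE with no start date and a complete stop date before first dose is flagged treatment-emergent, which is inconsistent with 16.7.2.1. It is probably rare, and it overcounts rather than hides harm.
- **Worsening.** This holds only if a grade change stays on the original AE record. If each change opens a new record, the flag already works.

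The effect falls on Table 3.002, on the assumption that displays stating no treatment-emergent restriction apply none. The number of affected subjects cannot be derived from the document, so the size can be given only per subject, as above. No stated decision rule is affected.

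**What to change.** In Section 16.4.2:

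1. Qualify the second bullet so that a missing AE start date leads to the flag unless the AE stop date is complete and falls before the study treatment start date.
2. Add a third route: the AE started before study treatment, and its grade increases on or after the treatment start date and no later than the treatment stop date + 45 days. Apply it where dated grade changes are held within an AE record.

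If the eCRF opens a new record at each grade change, one sentence saying so replaces item 2. If a record holds only its maximum grade with no date of change, item 2 cannot be programmed, and a footnote to Table 3.002 should say that worsening of pre-dose events is not captured.

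Under these rules record E drops out of Table 3.002, record F stays in, and record A enters if its grade change is dated. The reference in Section 8.1 should be redirected from 16.4.1.2 to 16.4.2 at the same time.

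The cost is two lines of text and slightly more programming in the AE derivation. Some treatment-emergent rates may become slightly less favourable.
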